#### 4.4 Secondary Efficacy Endpoints

Several secondary endpoints are being collected to gain a better understanding of what effect, if any, the interventions will have on each measure. We intend to evaluate these endpoints

(described below) to [REDACTED]. Refer to Section 9.3 for a detailed description of each endpoint. Changes from baseline will be evaluated as secondary efficacy endpoints for the following outcome measures:

- Durability of the treatment effect on average pain intensity [REDACTED]
- Durability of the treatment effect on average pain intensity [REDACTED]
- Pain interference (BPI-SF Question #9) [REDACTED]
- Pain disability (Pain Disability Index (PDI)) [REDACTED]
- Depression (Beck Depression Inventory (BDI-II)) [REDACTED]
- Analgesic usage [REDACTED]
- Prosthetic usage [REDACTED]
- Subject Satisfaction Survey

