**7.5.11 Visit 11 – EOT**

**8 Weeks Post Lead Placement: lead removal and end of treatment (EOT)**

The subject will return approximately 8 weeks after the initial lead placement. [REDACTED]

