**9.1 Primary clinical efficacy endpoint analysis**

[REDACTED]

The effectiveness of percutaneous Peripheral Nerve Stimulation (PNS) for the treatment of post-amputation pain will be assessed in the present study. The goal of the proposed [REDACTED] study is to determine if the investigational treatment produces pain relief that is clinically meaningful and greater than the placebo effect. To distinguish between the effect of the investigational treatment and the placebo effect, qualifying individuals will be randomized (1:1) to either Group #1 (Treatment) or Group #2 (Control). The groups will be identical except for whether active stimulation (Group #1) or sham stimulation (Group #2) is delivered during the first 4 weeks of the home trial. Both groups are expected to experience a similar placebo effect from the study procedures and use of the devices. In Group #1, subjects will experience both the placebo effect and the investigational treatment effect. During the sham stimulation phase in Group #2, subjects will experience only the placebo effect. Thus, if there is a difference between the mean improvements during sham stimulation and active stimulation, it can be attributed to the investigational treatment effects.

The null hypothesis ( $H_0$ ) is that the investigational treatment (Group #1, active simulation) is equal to the control (Group #2, sham stimulation) in providing pain relief. The alternative hypothesis ( $H_1$ ) is that Group #1 has a proportion of successes that is not equal to the proportion of successes of Group #2.

1.  $H_0$ : proportion of successes of Group #1 = proportion of successes of Group #2
2.  $H_1$ : proportion of successes of Group #1  $\neq$  proportion of successes of Group #2

If the proportion of successes of the investigational treatment is statistically significantly greater ( $p < 0.05$ ) than the proportion of successes of the control during the first 4 weeks of the home trial and the alternative hypothesis is accepted at the 0.05 level of significance, it will indicate that the investigational treatment is clinically significant and different than the placebo effect.

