The analysis of the durability of the treatment effect on average pain intensity compares the proportion of subjects who successfully achieve  $\geq 30\%$  reduction from baseline in Group #1 relative to that in Group #2, examining the statistical superiority of the proportion of successes of Group #1 over the proportion of successes of Group #2. The average post-amputation pain intensity scores will be determined for each subject using BPI-SF Question #5 with 1 week recall. For Group #1, the scores reported at Visit 2 (prior to lead placement) will be compared to the score for the same region(s) of pain at each monthly interval after the end of the 8-week home trial (i.e., during the monthly follow-up calls/visits from months 3-12 after start of therapy). For Group #2, the scores reported at Visit 2 (prior to lead placement) will be compared to the score for the same region(s) of pain during the final week of the 4-week sham period. To be considered a success, subjects must have clinically-significant reduction ( $\geq 30\%$ ) from baseline in all qualifying regions of pain, defined as regions of RLP and PLP with a baseline pain score  $\geq 4$  that received blinded treatment. The proportion of successes in Group #1 at each monthly visit will be compared to the proportion of successes in Group #2 at the end of the sham period. For each month, the null hypothesis is that there is no difference in success rates between the two treatment groups, versus the alternative hypothesis, that the success rates differ from one another. Testing will be conducted at the 0.05 level of significance.

- Pain interference (BPI-SF Question #9) at monthly intervals after start of therapy

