#### 9.4 Exploratory endpoint analysis

Exploratory endpoints will be analyzed to provide information on additional outcome measures and how the system and subject characteristics affect the outcome of the investigative treatment on post-amputation pain. For all endpoints, data will be collected as described in the Schedule of Procedures (Appendix A).

- Treatment effect in Group #2  
Group #2 will receive stimulation during the second half of the home trial (Weeks 5-8), and the proportion of successes and/or mean improvements in outcome measures during this phase will be compared to those during the sham stimulation phase. In addition, a repeated measures analysis may be conducted to determine the within-subjects improvement from sham to stimulation.

Global impression of change (Patient Global Impression of Change (PGIC))

Analyses of changes in average RLP

[REDACTED]

Analyses of changes in average PLP [REDACTED]

Analyses of changes in worst RLP [REDACTED]

Analyses of changes in worst PLP [REDACTED]

[REDACTED]

- Non-opioid medication usage

[REDACTED]

- Pain Catastrophizing Scale (PCS)

[REDACTED]

- Clinician Satisfaction Survey

[REDACTED]

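### Section 9.3 tests Group #1 results obtained after week 4 against Group #2's sham-period value, so elapsed time is mixed with the device effect

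*Combined protocol and SAP*

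**What the plan says.** Section 9.1 limits the sham control in time: the groups differ in whether "active stimulation (Group #1) or sham stimulation (Group #2) is delivered during the first 4 weeks of the home trial". It then argues that "if there is a difference between the mean improvements during sham stimulation and active stimulation, it can be attributed to the investigational treatment effects", on the ground that "Both groups are expected to experience a similar placebo effect from the study procedures and use of the devices".

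Section 9.4 says that "Group #2 will receive stimulation during the second half of the home trial (Weeks 5-8", and section 7.5.11 puts removal of the leads at the end of the home trial: "8 Weeks Post Lead Placement: lead removal and end of treatment (EOT". No sham group therefore exists after week 4, and neither group is scheduled for stimulation after week 8.

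Section 9.3 carries the sham-period value of Group #2 forward as the comparator. For monthly pain, the success proportion in "Group #1 at each monthly visit will be compared to the proportion of successes in Group #2 at the end of the sham period". The same construction is used for pain interference, PDI and BDI-II. The 8-week pain endpoint sets Group #1 averaged over eight weeks against Group #2 in weeks 1-4. The second MED analysis sets Group #1 in week 8 against Group #2 in week 4. The pain, interference, PDI and BDI-II analyses are framed as statistical superiority of Group #1. A 0.05 level is stated for monthly pain, interference, PDI and BDI-II. The week-8 MED analysis is a test of difference.

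On purpose, section 4.4 says the secondary endpoints are collected "to gain a better understanding of what effect, if any, the interventions will have on each measure". The sentence after that is partly redacted.

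**The concern.** The attribution argument in section 9.1 needs both groups to be read at the same time since lead placement. Randomization then makes everything except the stimulation comparable on average, including natural course, placebo response and regression to the mean. Once Group #1 is read later than Group #2, the difference also contains whatever would have changed over that interval without any device effect. Four sources are plausible here: the natural course of the pain, a placebo response that grows or fades, medication change (section 7.3 permits dose reductions and PRN use), and any slower component of regression to the mean. The visible text of section 9.3 has no adjustment for time and no caveat.

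At stake is what the durability results can support. A significant monthly result, reported as the plan frames it, would read as superiority over sham many months after treatment. The design has no sham observation at those times.

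**Working it through.** **1. The contrasts side by side (all section 9.3 except the primary, section 9.1)**

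| Endpoint | Group #1 reading | Group #2 reading | Concurrent? |
|---|---|---|---|
| Primary pain | weeks 1-4 | weeks 1-4 | yes |
| MED, first analysis | week 4 | week 4 | yes |
| Pain, 8-week home trial | weeks 1-8 | weeks 1-4 | partly |
| MED, second analysis | week 8 | week 4 | no |
| Pain, monthly | months 3-12 | final sham week | no |
| PDI | week 4, week 8, months 3-12 | end of sham | week 4 only |
| Interference, BDI-II | monthly after start of therapy | end of sham | month 1 only |
| Prosthetic use, 8 weeks | last week of stimulation | not stated | cannot be judged |

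**2. Time gaps**

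- Monthly pain and PDI: month 3 to month 12 against about month 1, so gaps of about 3 - 1 = 2 to 12 - 1 = 11 months. The end month is stated only for these two endpoints.
- MED: week 8 - week 4 = 4 weeks.
- 8-week pain: if diaries are daily throughout, 28 of 56 Group #1 days overlap with the sham window (50%), and the window midpoints are day 28 and day 14, so 14 days apart. These figures are nominal. The visible text does not show daily diaries throughout weeks 5-8, and section 9.1, whose method is reused, counts only days with all leads in place.

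**3. What the contrast estimates**

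Let m(t) be the expected outcome under sham at time t, and d(t) the device effect. The planned contrast has expectation

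[m(t) + d(t)] - m(week 4) = d(t) + [m(t) - m(week 4)].

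The bracketed drift term is zero at t = week 4. It is not identifiable afterwards, because nobody is on sham.

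**4. Illustration of size**

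The documents give no figure for these contrasts. The success rates behind the primary power statement are not visible, so that power cannot be reproduced, and it is not needed here.

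Inputs: 27 per group (section 6.2) and two-sided 0.05 (section 9.3). Assumed: no device effect, 20% success at week 4, and a later rate p. The visible text does not name the test for the secondary proportions, so two are shown.

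P(false Group #1 win) = sum of Bin(x1; n1, p) x Bin(x2; n2, 0.20) over all outcomes with two-sided p-value < 0.05 and x1/n1 > x2/n2.

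| Later rate p | n1 v n2 | Chi-square | Fisher |
|---|---|---|---|
| 20% (no drift) | 27 v 27 | 2.85% | 0.96% |
| 25% | 27 v 27 | 7.06% | 3.02% |
| 30% | 27 v 27 | 14.26% | 7.42% |
| 40% | 27 v 27 | 37.71% | 26.32% |
| 30% | 22 v 27 | 13.65% | 9.32% |

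The 22 v 27 row changes only the sample size and assumes no selective dropout. In the other direction, a fall to 10% with 27 v 27 gives a false Group #2 win in 18.64% (chi-square) or 7.57% (Fisher).

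For an endpoint compared as means, such as BDI-II (two-sample t-test assumed, 52 df), the noncentrality is drift in SD x sqrt(27/2). For 0.2 SD this is 0.2 x 3.674 = 0.735. Drift of 0.1, 0.2 or 0.3 SD gives a false Group #1 win in 5.49%, 10.77% or 19.00%, against 2.5% with no drift.

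These figures do not apply to MED, which is restricted to subjects on prescribed opioids at baseline and so has fewer than 27 per group unless every subject qualifies. They overstate the effect on 8-week pain, where part of the window is concurrent.

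**The case against.** The strongest defence is that this is a pilot study, the affected tests are secondary, and sham ends at week 4 by design. The end-of-sham value is then the only sham benchmark available, and section 9.3 states both time points openly. Section 4.4 describes the purpose as understanding effects, and redacted text may limit interpretation further. A fading placebo response would work against Group #1, which would make the contrast conservative for that mechanism. Regression to the mean from measurement noise appears at the first post-baseline reading, so much of it is already in Group #2's week-4 value. Section 7.3 also asks subjects not to raise routine doses.

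Much of this stands. It limits the weight of the point and narrows the list of mechanisms. It does not remove the problem: the superiority wording is visible, a benchmark from another time is not a control, and a redacted caveat could not make the readings concurrent.

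A reader might infer three stronger things that the documents do not support:

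- **That all of section 9.3, or the primary result, is compromised.** The week-4 readings are concurrent, and the 8-week pain endpoint is only partly affected.
- **That the bias favours the device.** It can run either way.
- **That the sponsor presents these tests as confirmatory.** The visible text does not use that word.

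**Conclusion.** The point holds for Group #1 readings taken after week 4. There the planned comparison does not isolate the device effect, and a significant result would not by itself support superiority over sham. Randomization still balances the groups at baseline, and a difference larger than any plausible drift would remain informative.

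The size is unknown. Under the assumed drift, the chance of a false Group #1 win runs from little above nominal (a 5-point rise with Fisher's test, 3.0%) to 38% (success doubling from 20% to 40%, chi-square). A reader might take the larger figures as this trial's error rate. They are not: the rates, drift and tests are all assumed.

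This should be fixed, because several secondary endpoints and all the monthly durability comparisons for pain depend on it. It leaves the primary analysis intact. No claim is made here about multiplicity or about rules for attrition.

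**What to change.** Amend section 9.3 as follows:

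- Limit between-group superiority tests to the concurrent sham window, weeks 1-4. This is already the plan for the primary endpoint and week-4 MED, and it keeps the month-1 readings of interference, PDI and BDI-II.
- After week 4, report Group #1 success proportions or mean changes from baseline with 95% CIs.
- Report Group #2 in the same way from its own start of active stimulation, noting that it has about 4 scheduled weeks of active stimulation against 8 in Group #1.
- Section 9.4 plans that in Group #2 "the proportion of successes and/or mean improvements in outcome measures during this phase will be compared to those during the sham stimulation phase". State that this within-group comparison is also confounded with time.
- If a contrast with the sham-period value is kept, label it descriptive and non-concurrent, and draw no superiority conclusion from it.
- State the Group #2 window for 8-week prosthetic usage, and apply the same rule to it.

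Cost: no new data and no change in conduct. The post-week-4 secondary endpoints lose their between-group p-values, including every planned between-group test for pain at months 3-12. The durability data are still reported in full.

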| 
Study Plan
                    | 
Amputees must have an average pain [REDACTED] to qualify
         Individuals with one or more lower extremity amputations reporting [REDACTED] pain [REDACTED] on the Brief Pain Inventory Short Form (BPI-SF [REDACTED]) will be considered for enrollment into the study. After informed consent is obtained, potential subjects will be evaluated for general eligibility. The individuals who satisfy the preliminary criteria will be asked to complete a [REDACTED] baseline diary to record their [REDACTED] post-amputation pain [REDACTED] for each amputated limb. Individuals must report [REDACTED] to qualify.
 
Percutaneous leads will be placed in the upper leg adjacent to the femoral and/or sciatic nerves
         Qualifying subjects will be randomized to either Group #1 (Treatment) or Group #2 (Control). In all subjects, leads will be placed percutaneously [REDACTED] [REDACTED] All subjects will be instructed to use the SPRINT Stimulator(s) continuously each day [REDACTED] during the [REDACTED] home trial. Initially, subjects will use the stimulation system [REDACTED]: in Group #1, the system will deliver electrical stimulation [REDACTED], while in Group #2, the system will deliver sham (placebo) stimulation. [REDACTED], Group #2 will begin receiving the investigative treatment
 |

[figure not shown]

Following the initial [REDACTED] home trial, subjects will continue using the stimulation system [REDACTED]. While Group #1 will continue receiving actual stimulation, Group #2 will begin receiving actual stimulation [REDACTED]. At the end of the home trial, subjects will return to the clinic to have their lead(s) removed. After lead removal, the subjects will be followed for 12 months.

**Daily medications affecting pain will be permitted at levels established during baseline and PRN (pro re nata) medications will be permitted as needed**

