Pain relief will be evaluated using the average pain intensity. All regions of post-amputation pain (RLP or PLP or both) that have intensities  $\geq 4$  on average during the baseline period and receive treatment with an investigational device will be used to assess the primary efficacy endpoint. All amputees will record two daily post-amputation pain scores (one daily score for RLP and one daily score for PLP) for each amputated leg in the 7-day diaries using BPI-SF Question #5. For each individual, the region(s) of post-amputation pain with a 7-day average  $\geq 4$  during baseline in a leg that receives blinded treatment from an investigational device(s) will qualify to be used in the determination of clinically-meaningful success for that subject throughout the study. Each amputee must have  $\geq 50\%$  reduction in all areas of qualifying RLP and PLP to be considered a success in the primary effectiveness endpoint analysis.

The primary endpoint of the study compares the proportion of subjects in Group #1 relative to that in Group #2 that achieve  $\geq 50\%$  reduction in all areas of qualifying post-amputation pain from baseline to the first 4 weeks of the home trial, examining the statistical superiority of proportion of clinical successes of Group #1 over the proportion of successes of Group #2. The post-amputation pain intensity scores will be determined for each subject by taking the mean of the daily average pain intensity (BPI-SF Question #5) reported in the 7-day diary at baseline compared to the mean score for the same region(s) of pain reported over the first 4 weeks of the home trial (*i.e.*, the average of all diary scores during this period). For each leg with leads, the average pain scores will only include the days when all leads are in place (e.g., if leads are placed in second leg during week 2 of home trial, then only the data from weeks 2-4 will be used). Data will be collected as described in the Schedule of Procedures (Appendix A).

**9.1.1 Baseline characteristics and changes in usage of medication affecting pain will be analyzed to determine how strong their relationships are with changes in pain intensity between baseline and EOT**

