The analysis of the treatment effect on pain interference compares the proportion of subjects who successfully achieve  $\geq 50\%$  reduction in average pain interference score in Group #1 relative to that in Group #2, examining the statistical superiority of the proportion of successes of Group #1 to that of Group #2. In Group #1, the baseline average pain interference score (BPI-SF Question #9) will be compared to the average pain interference score for the same region(s) at each monthly interval after start of therapy. In Group #2, the baseline average pain interference score will be compared to the score at the end of the 4-week sham period. To be considered a success, subjects must have  $\geq 50\%$  reduction in the average pain interference score of all qualifying regions of pain, defined as regions of RLP and PLP with an average baseline pain interference score  $\geq 4$  that received blinded treatment. The null hypothesis is that there is no difference in success rates between the two treatment groups (i.e., Group #1 at the monthly interval vs. Group #2 at end of sham period), versus the alternative hypothesis, that the success rates differ from one another. Testing will be conducted at the 0.05 level of significance.

- Pain disability (Pain Disability Index (PDI)) at monthly intervals after start of therapy

The analysis of treatment effect on pain disability compares the proportion of subjects who successfully achieve  $\geq 10$  point reduction in PDI scores from baseline in Group #1 relative to that of Group #2, examining the statistical superiority of the proportion of successes of Group #1 to that of Group #2. The baseline PDI score will be compared to the PDI score at end of first 4 weeks, at the end of the home trial, and at monthly intervals after end of therapy (3-12 months after start of therapy). In Group #1, the baseline PDI score will be compared to the PDI score at each monthly interval after start of therapy. In Group #2, the baseline PDI score will be compared to the score at the end of the 4-week sham period. To be considered a success, subjects must have a  $\geq 10$  point reduction in PDI. The null hypothesis is that there is no difference in success rates between the two treatment groups (*i.e.*, Group #1 at the monthly interval vs. Group #2 at end of sham period), versus the alternative hypothesis, that the success rates differ from one another. Testing will be conducted at the 0.05 level of significance.

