### 9.5 Per Protocol and Intent to Treat Analyses

Analyses of the primary and secondary effectiveness endpoints will be conducted on the intent-to-treat (ITT) population and the per-protocol (PP) population at each specified study interval defined as follows:

PP Population: The per-protocol population will consist of all randomized subjects who meet the following criteria:

- Were implanted [REDACTED]
- For Group #1 subjects: paresthesia coverage in the target areas.
- Have an adequate number of average pain intensity (BPI-5) scores in the diaries during the primary endpoint period (*i.e.*, first 4 weeks of home trial). These diaries must not be missing more than 50% of the pain scores to be included in the PP population.

[REDACTED]

- Continued study eligibility (subjects cannot have a change in medical status that would have otherwise excluded them from the study)

ITT Population: The intent-to-treat population will include all randomized patients who were implanted [REDACTED] that is, patients will be analyzed according to the treatment group to which they were randomized. Evaluable subjects are defined as those who were randomized and implanted with a lead.

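### PDI success needs a 10-point fall with no minimum baseline, and the interference rule does not classify subjects with no qualifying region

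*Combined protocol and SAP*

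**What the plan says.** Section 9.3 makes both measures responder endpoints, tested at the 0.05 level against the alternative that the success rates differ.

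- **Pain interference (BPI-SF Question #9).** Success is at least a 50% "reduction in the average pain interference score of all qualifying regions of pain". Those regions are "defined as regions of RLP and PLP with an average baseline pain interference score" of 4 or more that received blinded treatment.
- **PDI.** "To be considered a success, subjects must have a $\geq 10$ point reduction in PDI". No minimum baseline is given.
- **Primary endpoint, for comparison (Section 9.1).** The gate is on pain (BPI-SF Question #5). A region averaging 4 or more "during baseline in a leg that receives blinded treatment from an investigational device(s) will qualify to be used" in judging success.
- **Analysis sets (Section 9.5).** "Analyses of the primary and secondary effectiveness endpoints will be conducted on the intent-to-treat (ITT) population and the per-protocol (PP) population". Evaluable subjects are those randomized and implanted with a lead. No readable text limits either set by baseline interference or PDI.
- **Opioid usage, for contrast (Section 9.3).** This endpoint names its baseline subset: subjects on prescribed opioids at baseline.

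The readable inclusion and exclusion criteria (Synopsis and Section 7.4) set no minimum interference or PDI score. Several of them are partly redacted.

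**The concern.** A responder endpoint tells us about the device only through subjects who could fall on either side of the line. Each of these two rules has a group for whom that may not be so.

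Under the PDI rule, a subject who starts close to the bottom of the scale cannot fall by 10 points, yet stays in the denominator. Full resolution of disability would still be recorded as failure.

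Under the interference rule, a subject can qualify for the trial on pain and still have no region with interference of 4 or more, because pain and interference are different items. The success rule then refers to an empty set of regions. Section 9.3 does not say what to do with it.

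At stake are the size of the reported difference, the power of two secondary comparisons, and a coding choice that could be made after the data are seen.

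**Working it through.** **No planned figure to reproduce.** The readable power statement (Section 9.1.2: more than 90% power, 5% level, two-tailed) covers the primary endpoint only, and its success rates are not visible. What follows is illustration.

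**Inputs from the documents.** 27 subjects per group, 1:1 (Section 6.2); two-sided 0.05 (Section 9.3).

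**Assumptions.** PDI minimum of 0; success of 60% versus 20% among subjects able to respond; a share f whose outcome is fixed by baseline, equal in both arms.

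**Step 1: PDI floor.** Largest possible fall = baseline − scale minimum. With a minimum of 0, a baseline of 9 allows a fall of 9 at most, which is less than 10. Every baseline below 10 is therefore a certain non-responder in either arm.

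**Step 2: interference with no qualifying region.** Take a subject with one treated region, pain 6 and interference 3. The region counts for the primary endpoint and not for this one. If the rule is read as an average over qualifying regions, there is nothing to average. If it is read as every qualifying region improving, it is satisfied trivially. The text does not choose between these.

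**Step 3: effect on the rates.** Excluded: p1 and p2 unchanged, n becomes 27(1−f). Failures: p becomes (1−f)p. Successes: p becomes f + (1−f)p. Under the last two codings the difference becomes (1−f) × 40 points; under exclusion it stays at 40.

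**Step 4: power.** Power = Φ[(d − 1.96·SE0)/SE1], where d = p1 − p2, SE0 = √[2·p̄(1−p̄)/n], p̄ is the mean of p1 and p2, and SE1 = √{[p1(1−p1) + p2(1−p2)]/n}.

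At f = 20%:

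| Coding | p1 vs p2 | n per group | d | SE0 | SE1 | Power |
|---|---|---|---|---|---|---|
| None affected (f = 0) | 60% vs 20% | 27 | 0.40 | 0.1333 | 0.1217 | 87.3% |
| Excluded | 60% vs 20% | 21.6 | 0.40 | 0.1491 | 0.1361 | 78.6% |
| Failures | 48% vs 16% | 27 | 0.32 | 0.1270 | 0.1193 | 72.5% |
| Successes | 68% vs 36% | 27 | 0.32 | 0.1360 | 0.1288 | 66.1% |

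Example, failures: (0.32 − 1.96 × 0.1270)/0.1193 ≈ 0.597, and Φ(0.597) ≈ 0.725.

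At f = 10% the three codings give 83.4%, 80.5% and 77.2%. At f = 40% they give 65.5%, 54.3% and 45.0%.

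**Step 5: how many subjects?** The documents give no baseline distribution. If interference is taken as normal with mean 4 to 6 and SD 2 to 2.5, one score falls below 4 with probability from Φ((4−6)/2) = Φ(−1) = 16% up to Φ(0) = 50%. That is the share of subjects only if each has a single treated region. A subject with two regions is unscorable only if both are below 4. With mean 6 and SD 2, that is 0.159² = 2.5% if the regions are independent and 9.8% at a correlation of 0.8. With mean 4, it is 25% and 40%. So 16–50% is an upper bound under assumed means and SDs. No comparable share can be worked out for PDI.

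**The case against.** **The interference floor already handles low baselines.** This largely stands. The 4-or-more gate exists so that regions with little room to improve do not count, and excluding a subject with no such region is the natural reading. Section 9.5 does not forbid it: the opioid endpoint also has its own subset within the same framework. A reader might infer that 9.3 and 9.5 conflict, but the text supports only an unstated denominator.

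**Counting low-baseline PDI subjects as non-responders is a conservative convention.** This is fair. The rule is the same in both arms, so under randomization neither is favoured. It would be wrong to infer systematic bias; what can occur is dilution, plus chance imbalance at 27 per group.

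**The entry threshold is not visible.** This is correct. It is tempting to say that entry requires only pain of 4 or more, but the Synopsis reads "Amputees must have an average pain [REDACTED] to qualify", and the 4 in Section 9.1 is a region rule for the primary endpoint. The point needs only that no readable criterion sets a minimum interference or PDI.

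**The loss may be small, and does not occur under every coding.** Both parts stand. Exclusion keeps the 40-point difference and costs only sample size.

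**A mean comparison is a different estimand, and floor-level subjects dilute it too.** This also stands. It is a reason to add the mean comparison as support, not to replace the planned responder tests with it.

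**Conclusion.** The point holds, at minor severity. As written, the PDI rule keeps subjects with baseline below 10 as certain non-responders, provided the scale minimum is 0. The interference rule leaves subjects with no qualifying region unclassified, and that half is mainly missing detail.

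Under the assumed 60% versus 20% with a 20% fixed-outcome share, restricting the denominator gives 78.6% power, against 72.5% when such subjects count as failures: a gain of about 6 points. For interference, the three possible codings span 66.1% to 78.6%. The success rates and the share affected are assumptions, and the real share may be well below 20%. The primary endpoint is not affected.

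**What to change.** In Section 9.3:

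1. Keep both responder comparisons, but restrict them in both arms to subjects whose baseline allows a response: at least one treated region with interference of 4 or more, and PDI of 10 or more. Because the restriction uses baseline values only, the groups remain comparable by randomization.
2. Report the number excluded per arm for each endpoint.
3. Add, as a supportive analysis on all ITT subjects, an ANCOVA of mean interference and mean PDI at the end of the 4-week blinded period, adjusted for the baseline score. State how several regions are combined into one interference score.

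The cost is SAP wording and slightly more analysis of scores already planned for collection. The downside is a smaller denominator in the responder tables: about 21.6 per group instead of 27 if 20% are excluded.
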